7.1.3. ATTRITION

The determined sample size is 17 subjects per arm (34 total), but we will enroll 20 per arm (40 total) to allow for potential attrition.

8. ADVERSE EVENTS

An Adverse Event (AE) is defined as any new untoward medical occurrence or worsening of a preexisting medical condition in a clinical investigation participant administered study drug that does not necessarily have a causal relationship with this treatment. An AE can therefore be any unfavorable and unintended sign (such as an abnormal laboratory finding), symptom, or disease temporally associated with the use of investigational product, whether or not considered to be related to the investigational product.

A *non-serious adverse event* is an AE not classified as serious.

8.1. SERIOUS ADVERSE EVENTS

A Serious Adverse Event (SAE) is any untoward medical occurrence that at any dose:

- results in death
- is life-threatening (defined as an event in which the participant was at risk of death at the time of the event; it does not refer to an event which hypothetically might have caused death if it were more severe)
- requires inpatient hospitalization or causes prolongation of existing hospitalization (see **NOTE** below)
- results in persistent or significant disability/incapacity
- is a congenital anomaly/birth defect
- is an important medical event (defined as a medical event(s) that may not be immediately lifethreatening or result in death or hospitalization but, based upon appropriate medical and scientific judgment, may jeopardize the subject or may require intervention [e.g., medical, surgical] to prevent one of the other serious outcomes listed in the definition above. Examples of such events include, but are not limited to, intensive treatment in an emergency room or at home for allergic bronchospasm; blood dyscrasias or convulsions that do not result in hospitalization).
- Suspected transmission of an infectious agent (e.g., pathogenic or nonpathogenic) via the study drug is an SAE.

Although pregnancy and potential drug-induced liver injury (DILI) are not always serious by regulatory definition, these events must be reported within the SAEs timeline.

Any component of a study endpoint that is considered related to study therapy should be reported as an SAE (e.g., death is an endpoint, if death occurred due to anaphylaxis, anaphylaxis must be reported).

The following hospitalizations are not considered SAEs:

- a visit to the emergency room or other hospital department < 24 hours, that does not result in admission (unless considered an important medical or life-threatening event).
- elective surgery, planned prior to signing consent.
- admissions as per protocol for a planned medical/surgical procedure.
- routine health assessment requiring admission for baseline/trending of health status (e.g., routine colonoscopy).
- Medical/surgical admission other than to remedy ill health and planned prior to entry into the study. Appropriate documentation is required in these cases.

- Admission encountered for another life circumstance that carries no bearing on health status and requires no medical/surgical intervention (e.g., lack of housing, economic inadequacy, caregiver respite, family circumstances, administrative reason).
- Admission for administration of anticancer therapy in the absence of any other SAEs (applies to oncology protocols).

8.1.1.ADVERSE EVENT COLLECTION AND REPORTING INFORMATION:

- All Serious Adverse Events (SAEs) that occur following the subject's written consent to participate in the study through 30 days of discontinuation of dosing must be reported to BMS Worldwide Safety, whether related or not related to study drug. If applicable, SAEs must be collected that relate to any later protocol-specified procedure (e.g., a follow-up skin biopsy).
- Following the subject's written consent to participate in the study, all SAEs, whether related or not related to study drug, are collected, including those thought to be associated with protocolspecified procedures. The investigator should report any SAE occurring after these aforementioned time periods, which is believed to be related to study drug or protocol-specified procedure.
- An SAE report should be completed for any event where doubt exists regarding its seriousness.
- If the investigator believes that an SAE is not related to study drug, but is potentially related to the conditions of the study (such as withdrawal of previous therapy or a complication of a study procedure), the relationship should be specified in the narrative section of the SAE Report Form.

An appropriate SAE form (e.g., ex-US = CIOMS form or USA = Medwatch form) should be used to report SAEs to BMS. If you prefer to use your own institutional form, it must be reviewed by the BMS Protocol Manager prior to study initiation to ensure that, at a minimum, all of the data elements on the CIOMS form are present. Note: Please include the BMS Protocol number on the SAE form or on the cover sheet with the SAE form transmission.

- The CIOMS form is available at: http://www.cioms.ch/index.php/cioms-form-i
- The MedWatch form is available at: MedWatch 3500 Form
- The Sponsor will reconcile the clinical database AE cases (**case level only**) transmitted to BMS Global Pharmacovigilance ([contact]).
 - The Investigator will request from BMS GPV&E, [contact] the SAE reconciliation report and include the BMS protocol number every 3 months and prior to data base lock or final data summary.
 - GPV&E will send the investigator the report to verify and confirm all SAEs have been transmitted to BMS GPV&E.
 - The data elements listed on the GPV&E reconciliation report will be used for case identification purposes. If the Investigator determines a case was not transmitted to BMS GPV&E, the case should be sent immediately to BMS ([contact]).
- In addition to the Sponsor Investigator's responsibility to report events to their local HA, suspected serious adverse reactions (whether expected or unexpected) shall be reported by BMS to the relevant competent health authorities in all concerned countries according to local regulations (either as expedited and/or in aggregate reports).
- In accordance with local regulations, BMS will notify sponsor investigators of all reported SAEs that are suspected (related to the investigational product) and unexpected (i.e., not previously described in the IB). An event meeting these criteria is termed a Suspected, Unexpected Serious Adverse Reaction (SUSAR). Sponsor investigator notification of these events will be in the form of either a SUSAR Report or a Semi-Annual SUSAR Report.

- Other important findings which may be reported by BMS as an Expedited Safety Report (ESR) include: increased frequency of a clinically significant expected SAE, an SAE considered associated with study procedures that could modify the conduct of the study, lack of efficacy that poses significant hazard to study subjects, clinically significant safety finding from a nonclinical (e.g., animal) study, important safety recommendations from a study data monitoring committee, or sponsor or BMS decision to end or temporarily halt a clinical study for safety reasons.
- Upon receiving an ESR from BMS, the investigator must review and retain the ESR with the IB. Where required by local regulations or when there is a central IRB/IEC for the study, the sponsor will submit the ESR to the appropriate IRB/IEC. The investigator and IRB/IEC will determine if the informed consent requires revision. The investigator should also comply with the IRB/IEC procedures for reporting any other safety information.

SAEs, whether related or not related to study drug, and pregnancies must be reported to BMS within 24 hours \ 1 Business Day of becoming aware of the event. SAEs must be recorded on either CIOMS, MedWatch, or approved site SAE form.

Pregnancies must be reported and submitted to BMS. BMS will perform due diligence follow-up using the BMS Pregnancy Form which the investigator must complete.

SAE Email Address: [contact]

SAE [contact]

If only limited information is initially available, follow-up reports are required. (Note: Follow-up SAE reports should include the same investigator term(s) initially reported.)

If an ongoing SAE changes in its intensity or relationship to study drug or if new information becomes available, a follow-up SAE report should be sent within 24 hours \ 1 Business Day to BMS using the same procedure used for transmitting the initial SAE report.

All SAEs should be followed to resolution or stabilization. The causal relationship to study drug is determined by a physician and should be used to assess all adverse events (AE). The casual relationship can be one of the following:

- **Related:** There is a reasonable causal relationship between study drug administration and the AE.
- **Not related:** There is not a reasonable causal relationship between study drug administration and the AE.

The term "reasonable causal relationship" means there is evidence to suggest a causal relationship.

Adverse events can be spontaneously reported or elicited during open-ended questioning, examination, or evaluation of a subject (In order to prevent reporting bias, subjects should not be questioned regarding the specific occurrence of one or more AEs).

Non-serious Adverse Event

- Non-serious Adverse Events (AE) are to be provided to BMS in aggregate via interim or final study reports as specified in the agreement or, if a regulatory requirement [e.g., IND US trial] as part of an annual reporting requirement.
- Non-serious AE information should also be collected from the start of a placebo lead-in period or other observational period intended to establish a baseline status for the subjects.

Non-serious Adverse Event Collection and Reporting

The collection of non-serious AE information should begin at initiation of study drug. All non-serious adverse events (not only those deemed to be treatment-related) should be collected continuously through week 52 visit.

Non-serious AEs should be followed to resolution or stabilization, or reported as SAEs if they become serious. Follow-up is also required for non-serious AEs that cause interruption or discontinuation of study drug and for those present at the end of study treatment as appropriate.

Laboratory Test Abnormalities

All laboratory test results captured as part of the study should be recorded following institutional procedures. Test results that constitute SAEs should be documented and reported to BMS as such.

The following laboratory abnormalities should be documented and reported appropriately:

- any laboratory test result that is clinically significant or meets the definition of an SAE
- any laboratory abnormality that required the participant to have study drug discontinued or interrupted
- any laboratory abnormality that required the subject to receive specific corrective therapy.

It is expected that wherever possible, the clinical rather than laboratory term would be used by the reporting investigator (e.g., anemia versus low hemoglobin value).

AEs of Special Interest

In this study, the following adverse events are to be reported to BMS, regardless of whether these reports are classified as serious or unexpected:

Potential or suspected cases of liver injury including but not limited to liver test abnormalities, jaundice, hepatitis or cholestasis.

Pregnancy

If following initiation of the investigational product, it is subsequently discovered that a study participant is pregnant or may have been pregnant at the time of investigational product exposure, including during at least 5 half-lives after product administration, the investigational product will be permanently discontinued in an appropriate manner (e.g., dose tapering if necessary for participant).

The investigator must immediately notify [contact] of this event and complete one of the following forms within 24 hours of awareness of the event via either the CIOMS, MedWatch or appropriate Pregnancy Surveillance Form in accordance with SAE reporting procedures.

Protocol-required procedures for study discontinuation and follow-up must be performed on the participant.

Follow-up information regarding the course of the pregnancy, including perinatal and neonatal outcome and, where applicable, offspring information must be reported on the CIOMS, MedWatch, BMS Pregnancy Surveillance Form, or approved site SAE form. A BMS Pregnancy Surveillance Form may be provided upon request.

Any pregnancy that occurs in a female partner of a male study participant should be reported to BMS. Information on this pregnancy will be collected on the Pregnancy Surveillance Form. In order for Sponsor or designee to collect any pregnancy surveillance information from the female partner, the female partner must sign an informed consent form for disclosure of this information.

Other Safety Considerations

Any significant worsening noted during interim or final physical examinations, electrocardiograms, X-rays, and any other potential safety assessments, whether or not these procedures are required by the protocol, should also be recorded as a non-serious or serious AE, as appropriate, and reported accordingly.

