	After delivery of the systemic (IV) tPA/placebo, patients will continue IV unfractionated heparin therapy for at least 24 hours. If there is no evidence of active bleeding nor significant hemoglobin drop (i.e., $\geq 2 \text{ mg/dL}$), patients will be transitioned to standard dose apixaban, 10 mg twice-daily x one week followed by 5 mg twice-daily for at least 6 months. Some patients will require indefinite apixaban therapy based on patient-specific factors, including unprovoked nature of PE event, and/or persisting DVT/PE risk factors. Finally, consideration will be given for decreasing the apixaban dose to 2.5 mg twice-daily after 6 months. Apixaban was selected as the anticoagulant of choice due to its very favorable bleeding profile in large clinical trials, which is an important consideration when prescribing an anticoagulant following systemic thrombolysis.
	Within 24 \pm 8 hours post study drug infusion, a repeat chest CTA and echocardiogram will be performed. sPESI will also be calculated at this timepoint.

٦

	At Day 30, 180 and 365, all subjects will have clinic visits which will include a physical exam, repeat echocardiogram (at Day 30 & 180), 6 minute walk test (6MWT), quality of life questionnaires, assessment of adverse and bleeding events and a review of concomitant medications including compliance with apixaban. At Day 3, 7, 90 and 270, a remote health check will occur via telephone or email assessing adverse and bleeding events, alongside a review of concomitant medications (including an assessment of compliance with apixaban).
	If any subject experiences an adverse event (AE), the investigator may, at his or her discretion, decrease or discontinue the study drug or apixaban.
	The DMC will meet after 10 subjects are enrolled; bleeding and other complications will be reviewed. An interim analysis will occur after 20 subjects have completed Day 30. The DMC will meet again after 30 subjects have completed Day 30. Because it is a single-center study, the investigators and study coordinators will be acutely aware of all adverse events.
	The primary analyses will compare the clot lysis on CTA in treatment A at 24 hours post study drug infusion. See Section 7 for a complete discussion of the statistical analysis.

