5.4.1. TREATMENTS AND TIMING

SAFE-LYSE Flowchart of Procedures											
Procedures	Baseline up to 48 hours pre study medication	Day 0	Day 1	Day 2	Day 3 & Day 7	Day 30 + 15 days (Clinic Visit)	Day 90 + 15 days (Phone contact)	Day 180 + 15 days (Clinic contact)	Day 270 + 15 days (Phone contact)	Day 365 + 15 days (Clinic Visit)	ET1
Chest contrast- enhanced computed tomographic angiogram (chest CTA)	x		x								
Echocardiogram	x		х			х		х			х
Ultrasound of lower expremities to rule out DVT	x										
ECG	х										
Hemoglobin, hematocrit, platelet count	х	х	х	х		х					
BUN, creatinine	х	x	-x			х					
Liver Function Tests	х		-			х					
aPTT, PT and INR	x	х	-								
Troponin I (or Troponin T)	х										
BNP	х										
sPESI	х		х								
Quality of life questionnaires						х		х		x	x
Administration of tPA/placebo		х									
Administration of apixaban ³			х	х	x	х		х			
6 Minute Walk and Borg Dyspnea scale						х		х		x	х
Remote health checks (phone and email)							х		х		
Review of medications and adverse events, bleeding events and VTE events	x	x	x	x	x ⁴	x	x	x	х	x	x

¹Early Termination: Obtain if subject withdraws early

²Heparin duration up to clinician discretion but patient must be on for at least 24 hours after infusion of study drug.

³Could start as early as soon as 24 hours post treatment, contingent upon clinician discretion.

⁴72-hour assessment of AE will be conducted either in person or if discharged via telephone call. Day 7 follow up will be telephone call.

Anticoagulation

All subjects will receive unfractionated IV heparin per standard of care with a goal of aPTT of 1.5 - 2 times control which is approximately 50-70 seconds, upon established diagnosis of PE.

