- Within 24 ± 8 hours of discontinuing treatment, the subject will be assessed for improvement in PE signs and symptoms including sPESI score, repeat CT angiogram for determination of thrombus burden as measured by a Refined Modified Miller Score and RV/LV ratio, and an echocardiogram.
- Laboratory tests for Hgb, Hct, platelet count, aPTT, PT and INR, BNP, troponin, BUN and creatinine will also be obtained.
- Adverse events, VTE recurrence, and bleeding events will be recorded.

Day 2 Assessments

- Vital signs including temperature, respiratory rate, heart rate, blood pressure, and oximetry will be obtained.
- Laboratory tests for Hgb, Hct, platelet count, aPTT, PT and INR, BUN and creatinine will also be obtained.
- Adverse events, VTE recurrence, and bleeding events will be recorded.

Follow-up Clinic Visits and Subject Contact

- The subjects will be followed until Day 365 ± 15 days.
- A 72-hour follow-up assessment of Adverse Events will be conducted either in-person if the subject is still admitted at CSMC, or via telephone call if the subject is discharged.
- A Day 7 follow-up assessment of Adverse Events will be conducted via telephone call.
- The subject will return to the clinic Day 30, 180 and 365.
- The following assessments will be performed at follow-up clinic visits:
 - Echocardiogram at Day 30 and Day 180. Echocardiogram will be repeated at Day 365/EOT if last echocardiogram was abnormal.
 - Blood draw for laboratory tests, including hemoglobin, hematocrit, platelet count, BUN, creatinine, and liver function tests at Day 30.
 Physical exam and vital signs including respiratory rate, heart rate, blood pressure, temperature, and sPO2
 - o 6MWT with Borg score and requirement for oxygen therapy
 - Quality of life (QOL) as measured by the PROMIS PF-6 and Pulmonary Embolism Quality of Life (PEmb-QOL)
 - Adverse Events through 1 year follow-up.
 - Signs or symptoms of recurrent VTE
 - Changes in anticoagulant medications
 - Evidence of chronic thromboembolic disease or chronic thromboembolic pulmonary hypertension
- Phone calls for remote health checks will be conducted at Day 7, Day 90 ± 15 days and Day 270 ± 15 days.

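### Section 8.1.1 bars questions about specific adverse events without exempting the bleeding and DVT/PE endpoints, so at remote contacts non-severe bleeding and late outpatient DVT/PE rest on open-ended questioning alone

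*Combined protocol and SAP*

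**What the plan says.** Section 8.1.1 sets the method of collection: "Adverse events can be spontaneously reported or elicited during open-ended questioning, examination, or evaluation of a subject". It adds, with the stated aim of preventing reporting bias, that "subjects should not be questioned regarding the specific occurrence of one or more AEs". No exception is made for events that are also trial endpoints.

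Section 8 defines an adverse event as "any new untoward medical occurrence or worsening of a preexisting medical condition in a clinical investigation participant administered study drug". New bleeding and recurrent DVT/PE fall within that.

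The schedule names these events separately:

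- The Section 5.4.1 flowchart has a row "Review of medications and adverse events, bleeding events and VTE events", marked in all 11 columns from baseline to Day 365 and early termination.
- The Synopsis (Study Design and Methodology) says that at Days 3, 7, 90 and 270 "a remote health check will occur via telephone or email assessing adverse and bleeding events". It does not name VTE there.
- The Section 5.4.1 text for Days 1 and 2 says "Adverse events, VTE recurrence, and bleeding events will be recorded". For Day 7 it says only "A Day 7 follow-up assessment of Adverse Events will be conducted via telephone call", and the 72-hour text is equally general.
- For the clinic visits, Section 5.4.1 lists "Signs or symptoms of recurrent VTE".

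Section 1.2.2 makes recurrent DVT and PE a secondary endpoint, to be compared with placebo and with historic controls. Section 1.1 also plans major and minor bleeding rates out to 12 months.

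**The concern.** The method section tells staff not to ask about particular events. The schedule tells them to review two particular kinds of event each time. Nothing says which instruction governs when a subject is on the telephone or answering an email. One coordinator may ask directly about bleeding and leg or chest symptoms, while another asks only how the subject has been. The intensity of ascertainment then varies by person and by contact.

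What is at stake is the completeness of events that may reach the study only through what the subject says: bleeding below the GUSTO severe level, and DVT or PE arising after discharge. If some go unreported, their absolute rates come out low. Section 3.5 also has an interruption rule for apixaban triggered by significant bleeding that does not meet GUSTO criteria, and that rule presupposes that such bleeding is found.

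**Working it through.** The plan gives no figure for completeness of ascertainment, so the main check is a comparison of the sections.

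**Step 1. Does the bar reach these endpoints?** The Section 8 definition is broad enough to include them, and Section 8.1.1 contains no carve-out. Yes, as written.

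**Step 2. Which permitted routes remain at each contact?** Section 8.1.1 allows spontaneous report, open-ended questioning, examination and evaluation. From the flowchart and its footnotes:

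| Contact | Examination possible | Objective tests that could reveal bleeding or DVT/PE |
|---|---|---|
| Day 1 | Yes | Chest CTA, hemoglobin |
| Day 3 if discharged, Day 7 | No | None |
| Day 30 | Yes | Hemoglobin (last), echocardiogram |
| Day 90, Day 270 | No | None |
| Day 180 | Yes | Echocardiogram |
| Day 365 | Yes | Echocardiogram only if the last was abnormal |

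Leg ultrasound is scheduled at baseline only, and chest CTA at baseline and Day 1 only. At the remote contacts, what remains is spontaneous report and open-ended questioning.

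**Step 3. Which endpoints depend on that?** The primary safety endpoint (Section 1.2.3) is intracerebral hemorrhage, or bleeding with hemodynamic compromise requiring treatment, within 72 hours. That endpoint, stroke, death and rescue therapy mostly surface without prompting. Symptomatic PE recurrence needs objective confirmation, but after Day 1 a reported symptom is what would prompt the imaging. The exposed events are therefore non-severe bleeding and late outpatient DVT/PE.

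**Step 4. Scale, as illustration.** Table 1 in Section 7.1.2 reproduces. For n = 17 and incidence 0.05, x = 17 × 0.05 = 0.85. The Clopper-Pearson limits are the 0.025 quantile of Beta(0.85, 17.15) = 0.0007 and the 0.975 quantile of Beta(1.85, 16.15) = 0.274. The plan prints 0.001 and 0.274.

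Now assume a fraction s of events is detected. Expected observed events are 17 × 0.05 × s, and the chance of observing at least one is 1 − (1 − 0.05s)^17.

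| s (assumed) | Expected events | Chance of at least one |
|---|---|---|
| 1.00 | 0.85 | 58% |
| 0.90 | 0.77 | 54% |
| 0.75 | 0.64 | 48% |
| 0.50 | 0.43 | 35% |

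For one event assumed missed among all 40 subjects, 1/40 = 2.5% (exact 95% CI 0.1% to 13.2%) becomes 0/40 (upper limit 1 − 0.025^(1/40) = 8.8%). In an arm of 20, 1/20 (upper limit 24.9%) becomes 0/20 (upper limit 1 − 0.025^(1/20) = 16.8%).

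These figures show how sensitive the results are. They do not estimate how many events the rule would lose. The 5% is the plan's expectation for bleeding by Day 30, used here only as a convenient rate.

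**Step 5. Effect on each comparison.** If both arms have the same detection fraction s, true rates pA and pB are observed as s·pA and s·pB. The ratio is unchanged in expectation, and the difference shrinks to s·(pA − pB) without changing sign. The historic-control comparison has no such protection, because s applies to this trial only.

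**The case against.** The strongest reply is that nothing conflicts. The schedule says which events to capture and when; Section 8.1.1 says how. The schedule's verbs are review, assess and record, and no section orders a direct question or a checklist. Staff can ask openly and then probe what is reported. This stands in part: a reader might infer two strictly contradictory rules, and the documents do not support that. They do leave the two instructions unreconciled.

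Second, a reader might infer that at remote contacts events surface only if volunteered. That goes too far, because open-ended elicitation is expressly allowed. Section 6.1 also mentions questionnaires at the Day 90 and 270 calls, though it does not give their content.

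Third, bleeding and VTE are listed beside adverse events as separate items, so the bar may have been meant for other events only. That is a plausible intention. But the Section 8 definition includes them, and no text says they are exempt.

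Fourth, the VTE signs-and-symptoms item belongs to clinic visits, where examination is available, and hospital records are source documents under Section 6.2. Both points are correct. They limit the problem to remote contacts and to events that generate no record at the site.

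Finally, open-ended questioning is a legitimate way to limit reporting bias. Agreed; the difficulty is applying it without exception to pre-specified endpoints.

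**Conclusion.** The point holds as an unreconciled instruction with a limited reach. Followed as written, Section 8.1.1 leaves non-severe bleeding and late outpatient DVT/PE to open-ended questioning at the remote contacts. This can lower their absolute rates and bias the recurrence comparison with historic controls. The size and direction of that last bias also depend on how events were found in those controls, which the documents do not say.

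Three stronger readings are not supported:

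- **The primary safety endpoint is under-counted.** Its components are overt and would largely be detected anyway, as would stroke, death and rescue therapy.
- **One arm is favoured.** Section 4.3 blinds all study personnel except the research pharmacy, so missed events should be similar in proportion across arms, although a true absolute difference would be attenuated.
- **A number of lost recurrences can be calculated.** The 2.3% cited for apixaban in Section 1.1 is a primary efficacy outcome rate, with neither a definition as recurrence nor a time frame given there. The documents provide no detection fraction.

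Sample size, power, significance level and the primary efficacy endpoint are untouched.

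**What to change.** In Section 8.1.1, add a sentence exempting the pre-specified bleeding and DVT/PE endpoint events from the bar on specific questions. At each scheduled visit and remote contact, after the open-ended question, ask every subject in both arms the same short scripted questions on bleeding, symptoms of DVT or PE, and care received elsewhere. Keep open-ended questioning for all other adverse events. Align the 72-hour and Day 7 text and the Synopsis with the flowchart, so that each names the same event categories.

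The cost is one sentence, a short script and minor edits. No contact or test is added. Expect a few more minor bleeding reports, equally in both arms. Identical wording asked of blinded arms by blinded staff preserves the aim of limiting reporting bias.
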